### 3. Objectives & Specific Aims

**Objective:** This is a formative study to lay the groundwork for establishing a large cohort of incident colon cancer to examine the microbiome-immune relationship in colon cancer outcome. Our hypothesis is that colon cancer treatment, recurrence and survival are compromised by treatment-induced dysbiosis and dependent upon pre-treatment microbial structure. We plan to address this hypothesis with the following aims:

**Aim 1: Determine if the gut microbiome and microbial metabolites are altered in response to cancer treatment and correlate with CID incidence and severity in stage II/III colon cancer**

Sub-Aim1a: Quantify the gut microbiota prior to surgery and treatment, and at 3 time points during FOLFOX, and correlate with CID incidence and severity

Sub-Aim1b: Quantify microbial pathway abundance and fecal metabolite levels prior to, and during treatment, and determine their associations with incidence and severity of CID

Sub-Aim1c: Quantify circulating and tumor tissue cytokine levels prior to, and during treatment, and determine their associations with the gut microbiota, and incidence and severity of CID

**Aim 2: Determine if the dietary history or dietar intake during treatment is associated with CID incidence and severity in stage II/III colon cancer**

Primary outcomes: CID incidence and severity and gut microbiome and metabolome changes. The patients with colon cancer, serving as their own controls, will provide stool samples that enable clinicians to predict toxicity of anti-cancer therapy in stage II/III colon cancer patients.

Secondary outcomes: Circulating cytokines, dietary history and changes during treatment, stool index changes

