**The third through fifth study visits** (1 hour each) will take place on the 2nd(TD 15), 6th (TD 71) and 10th (TD 128) rounds of IV chemo of treatment (i.e. chemotherapy) at the BSWH center at which they are having their treatment. During this study visit, 2 blood vial samples will be taken as part of the routine clinical visit and the patient will be given two additional stool sample kits to take home to collect stool on the day before chemo starts and before chemo begins and the 2nd day and after their chemotherapy round is complete (i.e. if the infusion starts on Monday, the subject collect a stool sample on that Friday). After

each study visit, the patient will produce 2 stool samples (day before chemo starts and on the 2nd day after their chemo round ends) and drop it off at their treatment hospital or mail (FedEx) it into to the sequencing center at Baylor University. Again, they will be asked to complete the online 24 hour dietary recall (**ASA24**) at home within 72 hours of producing the stool samples. This is the same procedure that will be followed in the fourth and fifth study visits. During each of these visits, the REA or GI physician will ask about incidence and severity of chemotherapy induced diarrhea (**CTCAE – Gastrointestinal/Diarrhea, Grade 1-5**).

The REA will either call the subject or send a text message (if subject agrees) through Twillo after each visit to remind the subject of the days that stool collection and 24 hour (ASA24) recalls should occur.

The REA will obtain interval information from the participant according to the protocol and will provide subjects with stipends for each stool collection provided, which will include \$20 for each specimen collected (stool) up to \$160. If the patient was unable to provide a stool sample at the designated time point due to treatment side-effects they will still be given the compensation for completing the study. Thus, if patients complete all sample collections and all follow up visits, they may receive up to \$160.

Only [name] and the REA will have access to the data-collection sheets and registration forms that will be kept in a locked cabinet at the clinical site.

**Primary data endpoint:** At the end of the observational study we will assess incidence, duration and severity of chemotherapy-induced diarrhea.

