#### **4.4 Data Analysis.**

Classification of taxa associated with side effects or severity: Recently, in an animal model of colon tumorigenesis (AOM/DSS), investigators used the initial microbial community structure (16s rRNA sequencing) to predict tumor burden after exposure to various antibiotics during colon carcinogenesis. In order to conduct a similar analysis and reduce data dimensionality, we will first perform cluster modeling using Dirichlet multinomial mixtures (Holmes et al. 2012) to identify microbial clusters (community state types). To determine which taxa or taxonomic cluster are the best predictors of treatment side effects (CID, mucositis) and severity (stage 3-4), we will conduct 10-fold cross-validation using the RandomForest package (Version 3.6.4) in R (R-studio, Version 0.98.1091; Boston, MA). Specifically, 5,000 trees will be used and the parameter mtry will be set at 100. The taxa with the highest importance scores will be used for further analysis. This procedure will be tested by splitting the data into test and training sets, then running Random Forest using the same procedure described above on the training dataset and comparing the predictive accuracy of the top taxa (based on importance scores) in the test set. Based on this 10-fold cross-validation, we will be able to calculate sensitivity and specificity. These top taxa will then be used to generate receiver operator curves (ROC) and calculate area under the curve (AUC). Each microbial cluster or taxa will undergo independent logistic regression testing to calculate area under the ROC curve using Stata (v13). The command roccomp will be used to compare statistical difference between AUCs and determine the best combination of taxa for classification of CID or mucositis and for severity.

Microbiome-Diet Analysis: To evaluate the impact of diet on the stool and tissue microbiome, we will use the dietary analysis generated from the ASA24 and DHQIII, which includes the Healthy Eating Index (HEI). Prior to analysis, we will conduct normality testing for each variable using Shapiro-Wilk test. For any variables that do not pass, a logarithm transformation will be performed. In order to identify any potentially important diet or nutrient-microbiome associations, we will conduct correlation analysis between dietary macronutrients (carbohydrates, fats, proteins) or micronutrients (vitamins and minerals)

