and microbial clusters (community state types) at baseline using Kruskall-Wallis, and for individual taxa using Pairwise Spearman correlations. We will use PERMANOVA for comparing beta-diversity (weighted UniFrac distances) at baseline by levels of macro- and micronutrients. DESeq2, Kruskall-Wallis and Mann-Whitney tests will be conducted to identify significant differences in tissue and stool taxa or microbial clusters according HEI scores at baseline. The Benjamini and Hochberg false discovery rate (FDR) will be used to correct for multiple testing. Taxa or microbial clusters found to be significantly differentially abundant between treatment time points and baseline will be used to conduct 'random forest' modeling, as previously described, to identify dietary factors that best predict changes in these taxa or clusters. Additionally, we will investigate the tissue and stool microbiome-diet relationship using principal components analysis to identify significant trends among the dietary factors using coinertia analysis. To investigate the microbiome-diet relations during treatment, we will use the microbial clusters and calculate the  $\log_2$  fold change in the clusters from baseline. We will then determine how much the clusters change from baseline according to dichotomous values of macronutrients.

**Microbiome-treatment analysis:** To evaluate differential abundance comparing treatment time points to baseline (prior to surgery and post-surgery/pre-treatment), DESeq2 will be used to control operational taxonomic unit (OTU) over-dispersion between replicates; OTUs will be considered significantly differentially abundant between time points if the false discovery rate (FDR) corrected p-value is below 0.1. A change in relative abundance will be defined as a fold change between mean log relative abundance during treatment phase (week 4, 14, 24) and baseline (prior to surgery). Taxa found to be significantly differentially abundant between treatment time points and baseline (FDR corrected p-value  $<0.05$ ) will be put into an adjusted regression model to control for age, education, income level, marital status, and activity level, diet quality (HEI), tumor stage, medical history with p-values corrected for multiple hypothesis testing using FDR adjustment.

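### Section 4.4 describes no analysis of diet against chemotherapy-induced diarrhea (CID), so Aim 2 has no stated test; the nutrient-microbiome tests also name no adjustment for total energy intake

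*Protocol*

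**What the plan says.** Section 3 (Objectives & Specific Aims) has two numbered aims. The second is to "Determine if the dietary history or dietar intake during treatment is associated with CID incidence and severity in stage II/III colon cancer". Section 4.3 (Study procedures) makes CID the primary data endpoint: at the end of the study, "we will assess incidence, duration and severity of chemotherapy-induced diarrhea".

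Section 4.4, under Microbiome-Diet Analysis, states its purpose differently: "To evaluate the impact of diet on the stool and tissue microbiome, we will use the dietary analysis generated from the ASA24 and DHQIII". The steps that follow are:
- a normality test, after which "For any variables that do not pass, a logarithm transformation will be performed";
- a nutrient screen at baseline: "we will conduct correlation analysis between dietary macronutrients (carbohydrates, fats, proteins) or micronutrients (vitamins and minerals"; its targets are the community state types, tested by Kruskal-Wallis, and single taxa, tested by Spearman correlation;
- PERMANOVA, "comparing beta-diversity (weighted UniFrac distances) at baseline by levels of macro- and micronutrients";
- tests of taxa and clusters by Healthy Eating Index (HEI) score at baseline;
- random forest and co-inertia steps on dietary factors;
- change in clusters during treatment, by dichotomised macronutrients.

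Benjamini-Hochberg correction applies, with no threshold stated in that subsection. Total energy, nutrient density and energy residuals are not mentioned.

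**The concern.** There are two separate problems, and the first is the larger.

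**Aim and analysis do not meet.** Aim 2 has diet as exposure and CID as outcome, while the diet analyses in section 4.4 have microbial features as their target. If the plan is followed as written, nothing is computed for the second aim, although patients complete a long food-frequency questionnaire and repeated 24-hour recalls. If the model is written only after the data are seen, the choice among many nutrients, two instruments and several time points leaves wide room for selective reporting.

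**Nutrient tests without energy.** Intakes of most nutrients tend to rise and fall with the total amount eaten. A test of one nutrient against a taxon, with no account of energy, can therefore pick up total intake. Pairwise Spearman and Kruskal-Wallis tests, and a split at a macronutrient value, have no place for a covariate. FDR control does not help, because such an association is real; it is just not specific to the nutrient.

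**Working it through.** **Step 1. Does any analysis in section 4.4 pair diet with CID?**

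| Subsection of 4.4 | Predictors | Outcome or target | Diet tested against CID? |
|---|---|---|---|
| Classification of taxa (random forest, ROC, logistic) | taxa, clusters | CID, mucositis, severity | no |
| Microbiome-Diet | nutrients, HEI, dietary factors | taxa, clusters, beta diversity | no |
| Microbiome-treatment (adjusted regression) | taxa, with HEI as one control variable | not named | no; HEI is only adjusted for |
| Community state types | clusters over time | time point; plots against CID and mucositis | no |
| Metabolite-CID | metabolites | CID present or absent | no |
| Microbiome-Cytokine | cytokines | clusters, diversity | no |

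No row has a dietary exposure tested against CID.

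**Step 2. How much could total energy matter in the nutrient tests?** The protocol gives no figure to reproduce, and every correlation below is an assumption. Let a taxon correlate with total energy at r_TE and a nutrient with total energy at r_NE, with no other link between taxon and nutrient. The induced correlation is

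r = r_TE × r_NE,

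and the chance of p<0.05 (two-sided, Fisher z) is about Φ(√(n−3) × atanh(r) − 1.96).

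*Strong nutrient-energy correlation, n = 112 (planned recruitment).* Take r_NE = 0.35/√(0.35² + s²) with s = 0.35, 0.25, 0.15, which gives 0.71, 0.81, 0.92.
- Weakest case: r = 0.2 × 0.707 = 0.141; √109 × atanh(0.141) = 1.49; Φ(1.49 − 1.96) = 32%.
- Strongest case: r = 0.4 × 0.919 = 0.368; √109 × atanh(0.368) = 4.03; Φ(4.03 − 1.96) = 98%.
- Across r_NE from 0.71 to 0.92: 32–49% at r_TE = 0.2, 61–84% at 0.3, 86–98% at 0.4.

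*Wider range, by simulation, n = 100 (the stated minimum).* There were ten nutrients, 1,000 replicates, Spearman tests, no true nutrient effect, and Benjamini-Hochberg at an assumed 0.05. Each cell gives the share of nutrients with p<0.05 / the chance of at least one FDR-significant nutrient / the chance that all ten have p<0.05.

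| r_NE | r_TE = 0.2 | r_TE = 0.3 | r_TE = 0.4 |
|---|---|---|---|
| 0.4 | 12% / 18% / 0% | 21% / 36% / 0% | 32% / 60% / 0.1% |
| 0.6 | 21% / 30% / 0.3% | 41% / 62% / 2% | 62% / 88% / 10% |
| 0.8 | 31% / 35% / 5% | 63% / 73% / 24% | 87% / 94% / 58% |

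- Taxon unrelated to energy (r_TE = 0): 5–6% of nutrients have p<0.05, close to the nominal rate.
- After taking energy residuals, in every scenario: 4.7–5.5% have p<0.05, and the chance of any FDR-significant nutrient is 4.5–6.4%.

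The overall range of 12% to 98% joins the low end of the simulation (n = 100) to the high end of the Fisher calculation (n = 112).

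**The case against.** **On energy.** The protocol never says that intake is absolute or unadjusted. Its wording would also fit percent of energy or nutrient density, and the scaling of dietary variables is a detail that a statistical analysis plan, not shown here, may hold. The screen is exploratory and the study calls itself formative. All of this is fair. It is why the energy point is put as an adjustment that is not named, and as the lesser half.

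A reader might infer more than the documents support, in three ways:
- *That all diet analyses test nutrient amounts.* They do not. HEI, which the protocol calls diet quality, is tested as well, and the random forest and co-inertia steps take dietary factors jointly. Nothing calculated here shows what those steps would rank.
- *That eating less would look like an effect of every nutrient.* In the simulation all ten nutrients are flagged together in at most 10% of replicates at r_NE of 0.6 or less. It happens in more than half only at the strongest pair of correlations. With a taxon unrelated to energy there is no inflation.
- *That reduced intake on chemotherapy drives the result.* The Kruskal-Wallis, Spearman and PERMANOVA nutrient tests are placed at baseline, so chemotherapy cannot explain them. Only the dichotomised-macronutrient comparison is clearly a nutrient test during treatment.

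**On Aim 2.** The data to answer it are collected (DHQIII, ASA24, CTCAE grades), and a separate analysis plan might contain the model. So the study is not incapable of reporting on Aim 2; it is the plan in the protocol that does not do so. This is more than a detail left for later. Section 4.4 goes down to the number of trees, mtry and a Stata command, writes out CID models for taxa and metabolites, and gives diet a full subsection aimed at a different outcome.

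**Conclusion.** The point holds in two parts of unequal weight.

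1. Section 4.4 describes no analysis of a dietary exposure against CID, although Aim 2 asks exactly that. This is read directly from the text and rests on no assumption.
2. The nutrient-microbiome tests name no adjustment for total energy. If, and only if, a taxon or cluster is related to total intake, many nutrients could appear associated without a nutrient-specific effect. Under taxon-energy correlations of 0.2–0.4 and nutrient-energy correlations of 0.4–0.92, all assumed, about 12–98% of nutrients would be flagged at p<0.05. Energy adjustment brings this to about 5%. That intake enters unadjusted is inferred from the protocol's silence.

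The change should be made, but it does not call the conduct of the study into question.

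**What to change.** **Aim 2.** Add to section 4.4 a prespecified analysis of CID incidence (logistic model) and CTCAE diarrhea grade (ordinal model) on HEI and energy-adjusted intake from the pre-FOLFOX DHQIII. That exposure is measured before the outcome can affect it.

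**On-treatment diet.** Treat ASA24 intake as a secondary exposure and use only recalls that precede the graded episode, because diarrhea can itself change what is eaten. The timing needs care. Grades are asked at visits on treatment days 15, 71 and 128, and recalls are tied to stool collections around those same days. Without the recall linked to the day-before stool, the last one before the day-71 grade dates from about day 19, which is 71 − 19 = 52 days earlier. The recall window must also be reconciled: section 4.3 gives 72 hours of the stool sample in the visit descriptions but 24 hours under Dietary Analysis.

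**Nutrient-microbiome tests.** Use energy-adjusted nutrients (density or residuals), with total energy as its own variable. The HEI analyses can stay as they are.

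**Cost.** Protocol wording, slightly more analysis work and a few more tests under FDR. No new data and no added patient burden, assuming that total energy is part of the output of the two dietary tools already in use.

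### The comparison of microbial cluster change during treatment cuts continuous macronutrient intake into two groups, which discards information for no stated reason

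*Protocol*

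**What the plan says.** The point sits in Protocol section 4.4, Microbiome-Diet Analysis. Diet data come from the ASA24 recall and the DHQIII questionnaire. Each variable is to be checked with a Shapiro-Wilk test and logged if it fails.

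For the period on treatment, the plan computes the log2 fold change of the microbial clusters from baseline and then says: "We will then determine how much the clusters change from baseline according to dichotomous values of macronutrients". It names no test, cut-point or reason for having two groups.

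Other diet analyses in section 4.4 are not described as using two groups:
- At baseline, nutrients are related to taxa on a rank scale: "for individual taxa using Pairwise Spearman correlations".
- On treatment, a random forest is planned: "Taxa or microbial clusters found to be significantly differentially abundant between treatment time points and baseline will be used to conduct 'random forest' modeling". Its purpose is "to identify dietary factors that best predict changes in these taxa or clusters".
- The Healthy Eating Index (HEI) is a covariate in the adjusted regression of taxa that change on treatment: "diet quality (HEI), tumor stage, medical history with p-values corrected for multiple hypothesis testing using FDR adjustment".
- HEI is also tested at baseline: "DESeq2, Kruskall-Wallis and Mann-Whitney tests will be conducted to identify significant differences in tissue and stool taxa or microbial clusters according HEI scores at baseline".

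Aim 2 (section 3) asks whether diet "is associated with CID incidence and severity in stage II/III colon cancer", where CID is chemotherapy-induced diarrhea.

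**The concern.** Splitting a continuous exposure treats a patient just above the cut like one far above it, and separates two patients who lie either side of it with almost the same intake. A real gradient between intake and cluster change then becomes harder to detect. The answer can also move with the place of the cut.

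The choice sits badly with the rest of section 4.4. The planned log transformation has no effect on a median or other quantile split, because the same patients fall in each group. Baseline taxa are analysed with intake on its rank scale. Under Community state type modeling of treatment effect, the protocol says it wants to gain power because the sample is small, and there it already plans linear mixed models for repeated measurements. So a method that keeps the full scale is already in the plan. What is at stake is the sensitivity and stability of this one comparison.

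**Working it through.** **Inputs from the protocol.** Recruitment target 112 (section 4.3, Subject recruitment and enrollment); at least 100 stage II/III patients needed (Sample Population); significance level 0.05, stated for the taxon power calculation without sidedness (Taxonomic differential abundance analysis). The protocol gives no power, correlation or effect size for any diet analysis.

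**Assumptions supplied here.** Intake roughly normal, after logging if needed; linear relation; one comparison per patient with complete data; two-sided 0.05 with no multiplicity adjustment; r from 0.10 to 0.50.

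**The plan's own figure.** 100 × 1.10 = 110, and 100 / 0.90 = 111.1, which rounds up to 112. The target of 112 is consistent with about 100 needed, so both sizes are used.

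**Information kept by a split.** For a normal exposure with a share p below the cut q, the efficiency relative to the continuous term is φ(q)² / [p(1 − p)]. At the median this is (1/√(2π))² / 0.25 = 2/π = 0.637, a loss of 36%.
- Effective size: 112 × 0.637 = 71; 100 × 0.637 = 64.
- Uneven cuts: 40/60 keeps 62%, 30/70 keeps 58%, 25/75 keeps 54%, 20/80 keeps 49%.

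**Power.** Power = Φ(atanh(r)·√(n − 3) − 1.96). After a median split, r is replaced by r·√(2/π) = 0.798r.

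Worked case, r = 0.25 and n = 112:
- Continuous: atanh(0.25) = 0.2554; × √109 = 10.44 gives 2.667; less 1.96 gives 0.707; power 76.0%.
- Split: r = 0.1995; atanh = 0.2022; × 10.44 gives 2.111; less 1.96 gives 0.151; power 56.0%.

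| r | n=100 continuous | n=100 split | loss | n=112 continuous | n=112 split | loss |
|---|---|---|---|---|---|---|
| 0.10 | 16.6% | 12.1% | 4.5 | 18.1% | 13.0% | 5.1 |
| 0.15 | 31.9% | 21.9% | 10.0 | 35.1% | 24.1% | 11.1 |
| 0.20 | 51.5% | 35.4% | 16.1 | 56.2% | 39.0% | 17.2 |
| 0.25 | 71.1% | 51.2% | 19.8 | 76.0% | 56.0% | 20.0 |
| 0.30 | 86.2% | 67.2% | 19.0 | 89.8% | 72.2% | 17.6 |
| 0.40 | 98.7% | 90.3% | 8.4 | 99.3% | 93.2% | 6.1 |
| 0.50 | 100.0% | 98.6% | 1.4 | 100.0% | 99.3% | 0.7 |

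Losses are in percentage points, taken before rounding.

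**Check by simulation.** With 6,000 replicates per cell, a Pearson test was compared with a t-test on a median split. For r = 0.20 to 0.30 the loss is 16.8 to 20.5 points at n = 100 and 17.5 to 19.8 at n = 112.

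**Stricter thresholds.** The diet analysis plans Benjamini-Hochberg control. Taking 0.005 and 0.001 as stand-ins for an adjusted level, with n = 100, a test with 80% to 90% continuous power loses 25 to 33 points.

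**The case against.** The best case for leaving the text alone is that this is one secondary comparison in a study that calls itself formative, that it feeds no primary endpoint, and that the sentence names no test and may be meant descriptively. The cut-point could also stand in an analysis plan that is not shown. All of this bears on weight. It does not remove the point, because the protocol itself fixes a two-level exposure, and naming a cut later would not restore the information lost.

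A reader might infer more than the text supports, in four ways:
- **That diet on treatment is analysed only in two groups.** It is not. The random forest relates dietary factors to change from baseline, and HEI enters the adjusted regression. Neither is described as cut.
- **That Aim 2 loses power.** Aim 2 concerns diet and CID; the sentence concerns diet and microbial clusters.
- **That the HEI tests have the same flaw because Mann-Whitney and Kruskal-Wallis compare groups.** With clusters as the groups and HEI as the ranked response, no cut in HEI is needed, and DESeq2 accepts a continuous covariate. Only a rank test of taxa by HEI would need HEI groups, and none are defined. These tests are also at baseline, so the figures above do not carry over.
- **That PERMANOVA by nutrient level implies categories.** The wording can equally mean the amount of intake, and no categories are stated.

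**Conclusion.** The point holds for the one comparison of cluster change by two-level macronutrient intake during treatment. The 36% loss of information requires a median split, approximate normality and a linear relation; uneven cuts lose more.

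The power loss is conditional and is not a property of the plan, which states no effect size. It is about 16 to 20 points for r of 0.20 to 0.30 with 100 to 112 patients at an unadjusted two-sided 0.05. At that level it is smaller for weaker or stronger relations, and it can be larger under stricter thresholds. No figure in the protocol is contradicted. This is a cheap improvement to a secondary analysis and does not threaten the study's main conclusions.

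**What to change.** In section 4.4, Microbiome-Diet Analysis, replace the two-group comparison with a linear mixed model, across the treatment time points, of cluster log2 fold change on continuous macronutrient intake, logged where the planned Shapiro-Wilk step calls for it. Keep high and low intake groups for display only, with a cut set in advance, such as the median.

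The cost is the wording of one sentence. It needs no new data, visits or patients, and linear mixed models are already in the plan. The small downside is that a linear term assumes a shape; a quadratic or spline term can check it. On this point the HEI tests and PERMANOVA need no change.

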### Taxonomic differential abundance analysis

Power calculations for differential abundance analysis in human microbiome studies can be challenging, as there is limited data with highly consistent sample preparation available and uncertainty in the overall distribution of bacterial taxa throughout the human population. Recently, a CRC stool-based microbiome study of a large cohort was performed by Baxter and colleagues. This publicly available data serves as a potential resource for power-analyses by allowing for empirical calculation of the expected variability of taxa in both healthy and CRC-associated gut microbiomes.

We obtained the raw 16S rRNA sequence data from the Baxter study including patients with CRC (n=120) and healthy controls (n=172). After preprocessing and subsampling high-quality reads to an equivalent depth of 10,000 per sample, we identified 92 genus-level groups that each represented (on average) at least 0.25% of sequences from the CRC or healthy patient groups. We then computed the corresponding variance in relative abundance for each of these 92 taxa, and used the empirical values to perform a comprehensive power-analysis.

As expected, increased statistical power was found with higher abundance genera, so here we focus on power results for organisms reflecting an average of 0.25-1.0% of 16S sequences in the gut microbiome because detecting differences in these rare taxa may be critical to our study. Among the genera found at this low level, if we assume equal variance in two normally-distributed populations and require a significance level of  $\alpha=0.05$ , we expect that with a comparison of 40 vs 100 individuals, we will be able to detect a relative increase of 200% (e.g. 0.5% mean abundance increased to 1.5%), with a statistical power of 92.3% (*pwr.t2n.test* in R).

Considering the genera with average frequency  $>1\%$ , we estimate that with a 40 vs 100 sample comparison, we will be able to detect a relative increase of 200% (e.g. 1% mean abundance increased to 3%, or 2% mean abundance increased to 6%), with an expected statistical power of 99.6%.

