**Bioinformatics overview:** Read data will be filtered and analyzed using our validated 16S rRNA analysis pipeline in the [name] lab, which is housed on the Kodiak server at Baylor University. Sequencing analysis will be conducted using the QIIME bioinformatics pipeline and operational taxonomic unit (OTU) classification will be obtained. Specifically, 16S rRNA gene sequence data will be conducted by first demultiplexing fastq files generated by the MiSeq platform first screened for length and quality using QIIME. Reads containing more than five consecutive low quality base calls (Phred < Q20) will be truncated at the beginning of the low-quality region. Passing sequences will be required to have high quality base calls ( $\geq$  Phred Q20) along with a minimum of 75% of the read length to be included. After primer removal, final sequences containing ambiguous bases (Ns) or lengths less than 150bp will be removed. High quality sequences will be screened for spurious PhiX contaminant using BLASTN with a word size of 16. Reads will be assessed for chimeras using USEARCH61 (de novo mode, 97% identity threshold for clustering). Non-chimeric sequences will be screened for contaminant chloroplast and mitochondria using the RDP naïve Bayesian classifier, as well as non-specific human genome contaminant using Bowtie2 against the UCSC hg19 reference sequence. Finally, sequences will be evaluated for residual contaminants using BLASTN searches of the GreenGenes database (v13.5). High-quality passing sequences will subsequently be clustered into operational taxonomic units using the open-reference operational taxonomic unit (OTU) picking methodology implemented within QIIME using default parameters and the GreenGenes database (99% OTUs) supplemented by reference sequences from the SILVA database (v111). Prior to downstream diversity analyses, taxa with <5% abundance in all samples will be dropped from downstream analysis. Alpha diversity estimators and beta-diversity metrics will be computed in QIIME with differential abundance analyses performed in R. Mann-Whitney tests corrected for multiple testing (Benjamini–Hochberg (FDR)) will be used to conduct initial comparisons between time points.

*Metabolite Analysis:*

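### The printed power is for genus-level abundance, but differential abundance is declared on OTUs, so 92.3% and 99.6% are not the power of the planned OTU test

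*Protocol*

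**What the plan says.** **Power.** In the Protocol, under Taxonomic differential abundance analysis, the planners reanalysed a public 16S dataset: "we identified 92 genus-level groups that each represented (on average) at least 0.25% of sequences from the CRC or healthy patient groups". They then "computed the corresponding variance in relative abundance for each of these 92 taxa". The model is stated as "if we assume equal variance in two normally-distributed populations and require a significance level of" 0.05, "with a comparison of 40 vs 100 individuals". For genera at 0.25-1.0% the claim is that "we will be able to detect a relative increase of 200% (e.g. 0.5% mean abundance increased to 1.5"%), "with a statistical power of 92.3"%. For genera above 1% the figure is 99.6%. The summary table that follows uses the same two abundance bands.

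**Unit analysed.** Section 4.3, Bioinformatics overview, builds OTUs by open-reference picking with default parameters against "the GreenGenes database (99% OTUs) supplemented by reference sequences from the SILVA database (v111"). It then drops taxa that stay below 5% in all samples. It mentions no collapse to genus.

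**Decision rule.** Section 4.4, Microbiome-treatment analysis, runs DESeq2 to compare treatment time points with baseline: "OTUs will be considered significantly differentially abundant between time points if the false discovery rate (FDR) corrected p-value is below 0.1".

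**The concern.** The variability input belongs to one unit and the test to another. A genus is the sum of its OTUs. Its mean is larger than that of any one of them, and its relative variability is usually smaller, because variation in the parts partly cancels in the sum. Power worked out on genera therefore does not carry over to OTUs.

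Change in the gut microbiome is a primary outcome (section 3), and the sample size paragraph rests its figure of at least 100 patients on detecting differentially abundant microbes and metabolites. A reader who sees a null OTU result may set it against 92-99% power that was never calculated for OTUs, and take it as stronger evidence of no change than it is.

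**Working it through.** **1. Can the printed figures be reproduced?** Not forward, because the 92 genus variances are not printed. Back-solving is possible. With n1 = 40 and n2 = 100, df = 138 and the noncentrality is d × √(40 × 100 / 140) = 5.345 d. Two-sided at alpha 0.05, 92.3% needs d = 0.638 (noncentrality 3.41) and 99.6% needs d = 0.869 (noncentrality 4.64).

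One common d does not fit the table. Halving 0.638 for a 100% increase gives 39.5% power, against 67.2% printed. The table does fit as power averaged over genera with a lognormal spread of SD/mean:

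| Band | Fitted median SD/mean | Log-SD | Largest deviation |
|---|---|---|---|
| 0.25-1.0% | 2.13 | 0.51 | 1.1 points |
| >1% (300% row not fitted) | 1.32 | 0.45 | 0.4 points |

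This is a back-fit, not a reproduction. It shows that the table is coherent as average genus-level power at a per-test alpha of 0.05. No arithmetic error in it is shown.

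**2. Direction of the noise.** Let a genus G be the sum of OTUs with means m_i and standard deviations s_i. The SD of a sum cannot exceed the sum of the SDs, so

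SD(G)/mean(G) ≤ Σ (m_i / mean(G)) × (s_i / m_i).

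The genus SD/mean is at most the abundance-weighted mean SD/mean of its OTUs. For an equal relative shift in every OTU, the OTUs are on average at least as noisy, so power tends to be lower.

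**3. Size if the shift is shared (assumed range).** OTU variances are not given. Multiply the fitted genus SD/mean by an assumed factor, at 40 vs 100, two-sided alpha 0.05:

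| Factor | 0.25-1.0%, +200% | 0.25-1.0%, +100% | >1%, +200% |
|---|---|---|---|
| 1 | 93% | 66% | 99% |
| 1.25 | 87% | 54% | 98% |
| 1.5 | 80% | 45% | 96% |
| 2 | 66% | 31% | 89% |
| 3 | 45% | 18% | 71% |

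The printed table gives a second illustration, if an OTU is assumed to be as variable as a genus of the same mean. A genus above 1% that splits into OTUs at 0.25-1.0% moves from 99.6% to 92.3% (+200%), from 88.8% to 67.2% (+100%) and from 54.9% to 30.6% (+50%). No power is printed below 0.25%.

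**4. Size if one OTU carries the shift.** Take a genus just above 1% made of two equal OTUs, with the whole change in one of them, and keep the same assumption on variability. A genus increase of 100% (88.8%) becomes an OTU increase of 200% in the lower band (92.3%). A genus increase of 50% (54.9%) becomes an OTU increase of 100% (67.2%). Per-test power rises in both cases.

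**The case against.** The strongest reply is that the unit is only one of several differences between the power calculation and the OTU test, and that the loss is not proven. Most of this stands.

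- The calculation compares independent groups by t-test at alpha 0.05. The planned test compares repeated samples from the same patients by DESeq2 at FDR below 0.1. Moving to genus level would not by itself make the printed power apply.
- The sample size paragraph ties the 100 patients to taxa associated with chemotherapy-induced diarrhoea, not to shifts between time points. The protocol does not claim 92-99% power for treatment-related shifts.
- A reader might infer that every OTU is tested with less power than printed. Step 4 of the working shows a case where power is higher, so the documents do not support that.
- A reader might infer that more hypotheses must enter the FDR correction. An OTU averaging below 0.25% survives the 5% filter only if it reaches 5% in some sample. The number of OTUs left is unknown and may not exceed 92.
- A reader might infer that reads are clustered at 99% identity. That percentage describes the reference database; the clustering threshold is left to default parameters. The mismatch does not depend on it.

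It can also be said that taxonomic rank is a detail for the SAP, and that the study is formative. That carries less weight here: the protocol itself fixes genus for the power and OTU for the decision rule, so the inconsistency is already in its text.

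**Conclusion.** The mismatch holds and can be read directly from the protocol. The printed 92.3% and 99.6% are genus-level figures and are not the power of the planned OTU test.

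The size of the difference cannot be derived from the protocol. If the OTUs of a genus shift by similar relative amounts, power will on average be lower; the falls tabulated above rest on an assumed ratio of OTU to genus SD/mean. If one OTU drives the shift, power may be higher. The 5% filter limits how many sparse OTUs are tested, but it does not restore the printed figures: an OTU that reaches 5% in one sample can still have a low mean and a large variance.

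**What to change.** In the sample size paragraph and the power section, state that the printed power is genus-level and does not apply to the OTU test. Recompute power from OTU-level variances in the same public dataset, after the planned 5% filter and under the planned comparison and FDR rule.

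As well or instead, add to the Microbiome-treatment analysis in section 4.4 a DESeq2 analysis of OTU counts summed to genus. Name it as the analysis matched to the unit of the power calculation, and keep the OTU analysis alongside, since a shift confined to one OTU could be diluted at genus level. If only this second step is taken, the text should still say that the printed power assumes independent groups, a t-test and a per-test alpha of 0.05.

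The cost is a modest amount of extra analysis, one aggregation step in the existing pipeline, some rewording and possibly a less favourable stated power.
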